9.1.1 Dose Modification

Dose delays and modifications will be made as indicated below. The descriptions and grading scales found in the revised NCI Common Terminology Criteria for Adverse Events (CTCAE) version 4.03 will be utilized for dose delays and dose modifications. A copy of the CTCAE version 4.03 can be downloaded from the CTEP website:

http://ctep.cancer.gov/protocolDevelopment/electronic_applications/ctc.htm.

1. If any patient experiences a CTCAE grade 3 or intolerable grade 2 adverse event related to osimertinib, dosing will be interrupted and supportive therapy administered as per institutional standard. Patients will not be permitted to restart osimertinib until toxicities have resolved to CTCAE grade ≤ 1 .
2. If grade 3 or intolerable adverse event does not resolve with 21 days, patient should permanently discontinue study therapy
3. If first grade 3 or intolerable grade 2 adverse event which resolves within 21 days patient may restart at 80 mg dose level or 40 mg dose delay (at the discretion of the treating physician)
4. If second grade 3 or intolerable grade 2 adverse event which resolves within 21 days patient must have dose reduced to 40 mg daily
5. If patient is on 40 mg dose level and experiences a grade 3 or intolerable grade 2 adverse event patient must discontinue study therapy
6. Patients experiencing corneal ulceration (any grade), interstitial lung disease (ILD), and QT_c interval prolongation with signs/symptoms of serious arrhythmia will permanently discontinue the osimertinib.
7. For patients with grade 3 QT_c prolongation dose reduction to 40 mg daily is mandatory

Patients who are unable to remain on study therapy because of toxicity should be considered for treatment, as per institutional standard.

Dose reduction schema for grade 3 or intolerable grade 2 adverse events.

For specific management other than pulmonary, QT_c prolongation, and corneal ulceration or grade 3 ophthalmologic adverse events please refer to table and text

[figure not shown]

TABLE 2: DOSE REDUCTION

Dose level	Osimertinib dose	Schedule
“0”	80 mg	Daily
“-1”	40 mg	Daily

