Grade 2 intolerable or grade 3	Study treatment interruption for up to 21 days	Topical antibiotic bid and vinegar soaks as outline above Topical silver nitrate weekly Consider nail avulsion or removal
Grade 4	Discontinue study treatment	
Hepatic Transaminases and/or total bilirubin: please refer criteria for Hy's law provided in appendix 3		
Grade 1	None	Observation
Grade 2	None	Observation
Grade 3	Study treatment interruption for up to 21 days	Observation until laboratory values return to Grade 1
Grade 4	Discontinue study treatment	
Pulmonary Events if possibly Interstitial Lung Disease (ILD)		
All Grades	Temporarily interrupt study treatment pending the diagnostic evaluation. If the pulmonary adverse event is felt to be related to osimertinib, then permanently discontinue osimertinib.	Unexplained dyspnea, either new or progressive, should be thoroughly evaluated. Where ILD is suspected, administer corticosteroids at a dose of 1 to 2 mg/kg/day prednisone equivalents for Grade 2 or greater pneumonitis, followed by corticosteroid taper.
Cardiac		
Grade 3	QTc interval greater than 500 msec on at least 2 separate ECGs	Withhold osimertinib until QTc interval is less than 481 msec or recovery to baseline if baseline QTc is greater than or equal to 481 msec, then restart at a reduced dose (40 mg)
Grade 4	QTc interval greater than 500 msec or > 60 msecs from baseline and with signs/symptoms of serious arrhythmia	Permanently discontinue osimertinib
Management of elevated creatine kinase: please check for drug-drug interactions and refer to appendix 2 for potential drug-drug interactions		
Grade 1	None	Observation (assess for drug-drug interactions contributing to elevation. Please refer to appendix 2)
Grade 2	None	Observation (assess for drug-drug interactions contributing to elevation. Please refer to appendix 2)

40

The information contained in this document is regarded as confidential, and may not be disclosed to another party unless such disclosure is required to initiate the study, to conduct study-related activities, or to comply with national, state, or local laws and regulations. Written authorization from the coordinating site and sponsor is required for disclosure otherwise.

Grade 3	Study treatment interruption for up to 21 days	Observation until laboratory values return to Grade 1 (assess for drug-drug interactions contributing to elevation. Please refer to appendix 2)
Grade 4	Discontinue study treatment	Discontinue study treatment
Ocular		

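### Section 9.1.1 stops osimertinib permanently for any ILD, Table 3 only if the event is judged drug-related; and the grade 3 QTc rules do not say what applies to a patient already on 40 mg

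*Combined protocol and SAP*

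**What the plan says.** Section 9.1.1 gives a numbered list of dose rules.

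- Item 5: "If patient is on 40 mg dose level and experiences a grade 3 or intolerable grade 2 adverse event patient must discontinue study therapy". It makes no exception for QTc.
- Item 6: "Patients experiencing corneal ulceration (any grade), interstitial lung disease (ILD), and" QTc "interval prolongation with signs/symptoms of serious arrhythmia will permanently discontinue the osimertinib". For ILD it states neither a grade nor a causality condition.
- Item 7, for grade 3 QTc prolongation: "prolongation dose reduction to 40 mg daily is mandatory". It does not mention the dose the patient is on.

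Table 2 has two dose levels only, 80 mg and 40 mg.

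Table 3, in Section 9.1.2, returns to the same events. Its row headed "Pulmonary Events if possibly Interstitial Lung Disease (ILD" applies to all grades. It first says "Temporarily interrupt study treatment pending the diagnostic evaluation", then "If the pulmonary adverse event is felt to be related to osimertinib, then permanently discontinue osimertinib". It has no sentence for an event judged unrelated. The Cardiac grade 3 row (QTc above 500 msec on at least two ECGs) withholds treatment until the interval recovers, "then restart at a reduced dose (40 mg" being the dose named.

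**The concern.** Both places instruct sites on when treatment ends for good, and for two kinds of patient they do not give one answer. Sites could handle identical patients differently according to the page they read. For ILD this is a safety matter: Section 2.4 reports fatal ILD in 0.6% of 833 patients. The QTc issue carries less weight, because the same section reports no evidence of increased arrhythmia risk.

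There is also a modest analysis consequence. Section 22.4.2 counts a patient who stops therapy before response is confirmed as a non-responder, so the rule a site follows can settle that patient's primary outcome. The reported rate of discontinuation for toxicity would also mix two rules.

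**Working it through.** The main check sets the two texts side by side.

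| Situation | Section 9.1.1 | Table 3 | Result |
|---|---|---|---|
| Possible ILD, in work-up | Item 6 not clearly triggered | Interrupt | Compatible |
| Confirmed ILD, judged related | Permanent stop | Permanent stop | Agree |
| Confirmed ILD, attributed to another cause | Permanent stop | No permanent stop; next step not written | Differ |
| Corneal ulceration | Permanent stop | Permanent stop | Agree |
| QTc prolongation with signs of serious arrhythmia | Permanent stop | Permanent stop | Agree |
| Grade 3 QTc on 80 mg | Item 7: to 40 mg | Withhold, then 40 mg | Agree |
| Grade 3 QTc on 40 mg | Item 5: discontinue; item 7: to 40 mg | Withhold, then 40 mg | Not settled |

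Only the third and last rows are at issue. The last row's tension already exists inside Section 9.1.1, between items 5 and 7. The protocol itself produces such patients: a first grade 3 QTc event puts the patient on 40 mg, and a recurrence then meets both rules.

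Patients in the third row can be enrolled. Section 5.2 allows radiotherapy completed more than 14 days earlier and up to two prior systemic lines, and Sections 1.2 and 2.1 list immunotherapy among standard treatments. Exclusion 16d removes past or active ILD and steroid-treated radiation pneumonitis, which narrows the group without emptying it.

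**Expected counts.** Inputs: 37 patients (Section 22.4.2); ILD or ILD-like reactions in 3.5%, and QTc above 500 msec in 0.7% (6/833 = 0.72%), both from Section 2.4.

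- ILD-like: 37 × 0.035 = 1.3 expected.
- QTc above 500 msec: 37 × 0.007 = 0.26 expected.

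These count all such events, not the disputed ones.

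- ILD: let u be the share attributed to another cause. The affected number is 1.3 × u, anywhere from 0 to 1.3. The documents do not give u. The source figure counts adverse reactions; if that already leaves out events judged unrelated, it does not bound them.
- QTc: let q be the share occurring in patients already on 40 mg. The affected number is 0.26 × q. If q equals the 2.9% dose-reduction rate in the osimertinib arm of AURA3 (Section 2.4) and the two are independent, 37 × 0.007 × 0.029 = 0.0075. That leaves out recurrence after a QTc-driven reduction, for which no rate is given. The range is therefore about 0.0075 to 0.26.

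**Timing against response confirmation.** Scheduled CT falls on day 1 of cycle 3 (2 × 28 + 1 = day 57) and day 1 of cycle 5 (4 × 28 + 1 = day 113). Median ILD onset of 2.7 months (Section 2.4) is 2.7 × 365.25/12 = 82 days. On the scheduled calendar, a patient with onset at the median could have a first response not yet confirmed. One patient changes the trial's conclusion only at the boundaries: 3 versus 4 of 17, or 10 versus 11 of 37.

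**The case against.** A reader might infer that the two texts give opposite orders, one to stop and one to resume. The documents do not support that. Table 3 never tells a site to resume after unrelated ILD; resumption is at most implied by the interruption being temporary. Item 7 says nothing about restarting.

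The texts can also be read as stages: the table for suspected events, item 6 for confirmed ILD. This narrows the conflict but does not remove it, because item 6 turns on diagnosis and the table on attribution. Nor does the relatedness condition in item 1 clearly carry over. Item 1 concerns grade 3 or intolerable grade 2 events, whereas item 6 takes in corneal ulceration of any grade and ILD with no grade stated.

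On QTc the objection is stronger. Reducing to 40 mg presupposes a patient above 40 mg, and Table 2 has no lower level, so item 5 may be meant to govern a patient already there. On that reading nothing conflicts. It is a sensible reading, but neither item 7 nor the Cardiac row states it.

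On precedence, Section 9.1.2 calls itself guidance while Section 9.1.1 uses mandatory wording. That is a signal, not a rule, and Table 3 has its own dose-modification column. The cross-reference in Section 9.1.1 sets pulmonary, QTc and corneal events apart from those it sends to the table and text, yet Table 3 has rows for them. It may be the caption of a dose-reduction figure that is not shown, so little can be built on it.

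Finally, the chance of seeing at least one event of any kind, 1 − 0.965^37 = 73% for ILD and 1 − 0.993^37 = 23% for QTc, might be taken as the chance of meeting the conflict. It is not: the disputed cases are a subset. QTc detection is further limited because ECGs after screening are discretionary (Table 4, note 10).

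**Conclusion.** The ILD inconsistency stands: the permanent stop is unconditional in item 6 and conditional on relatedness in Table 3, and the two part for confirmed ILD attributed to another cause. The QTc point stands only as an unstated exception for a patient already on 40 mg, partly within Section 9.1.1, and not as a direct opposition. No readable sentence sets precedence; the figure that is not shown cannot be judged.

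The numbers are small and cannot be pinned down: an unknown part of about 1.3 ILD-like events, and at most about 0.26 patients for QTc. Both assume that rates from the cited AURA patients, treated in second line or later, carry over to this trial. The effect on the response rate is likely negligible unless the count sits on a decision boundary. The reason to act is consistent handling of safety stops. It should be corrected as a clarification, chiefly for ILD.

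**What to change.** Three edits are needed:

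1. Reconcile item 6 of Section 9.1.1 with the pulmonary row of Table 3, so that both state the same condition for a permanent stop and the table says what follows when that condition is not met.
2. Reconcile items 5 and 7 and the Cardiac grade 3 row for a patient already on 40 mg.
3. Add one sentence saying whether Section 9.1.1 or Table 3 governs pulmonary and QTc events.

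Which rule applies is for the sponsor's clinicians; this review takes no position on it. The cost is a few words in two table rows and three list items, plus the usual amendment approval. Sample size, visits and analysis do not change.

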9.1.2 Management of adverse effects

Symptom-specific toxicity management

Guidance for toxicity management will be as indicated below for patients enrolled, and investigators should manage toxicities per institutional standards and the specific clinical circumstances. Other toxicities should be managed as per institutional standards or at the discretion of the investigator.

For additional details, please refer to the table and text below:

TABLE 3 DOSE MODIFICATION GUIDELINES

NCI-CTCAE (v4.03) Grade	Dose Modification	Guideline for Management
Diarrhea		
Grade 1	None	Consider loperamide (4 mg at first onset, followed by 2 mg q2-4 hours until free of diarrhea for 12 hours, maximum daily dose of 16 mg/day).
Grade 2	None	Loperamide (4 mg at first onset, followed by 2 mg every 2-4 hours until free of diarrhea for 12 hours, maximum daily dose of 16 mg/day).
Grade 3 or intolerable grade 2	Hold study treatment for up to 21 days	Dose modification as noted, with supportive care per PI discretion.
Grade 4	Discontinue study treatment.	Supportive care as per intuitional standard
Rash		
Grade 1 and 2 tolerable rash	None	Any of the following, at the discretion of the investigator: 
 1. Oral antibiotics (tetracycline, minocycline, doxycycline) 2. Topical clindamycin, diphenhydramine, topical corticosteroids or emollient cream
Grade 2 intolerable or grade 3 rash	Study treatment interruption for up to 21 days	Manage as described above with both oral antibiotics and topical agent. Oral corticosteroids may be considered at the discretion of the investigator.
Grade 4	Discontinue study treatment	Manage as described above with both oral antibiotics and topical agent. Oral corticosteroids may be considered at the discretion of the investigator.
Paronychia		
Grade 1	None	Topical antibiotic bid and vinegar soaks (soaking finger or toes in a 1:1 solution of white vinegar in water for 15 minutes every day)
Grade 2	May continue at current dose or dose reduce at the discretion investigator	Topical antibiotic BID and vinegar soaks as outline above Topical silver nitrate weekly

39

The information contained in this document is regarded as confidential, and may not be disclosed to another party unless such disclosure is required to initiate the study, to conduct study-related activities, or to comply with national, state, or local laws and regulations. Written authorization from the coordinating site and sponsor is required for disclosure otherwise.

Grade 2 intolerable or grade 3	Study treatment interruption for up to 21 days	Topical antibiotic bid and vinegar soaks as outline above Topical silver nitrate weekly Consider nail avulsion or removal
Grade 4	Discontinue study treatment	
Hepatic Transaminases and/or total bilirubin: please refer criteria for Hy's law provided in appendix 3		
Grade 1	None	Observation
Grade 2	None	Observation
Grade 3	Study treatment interruption for up to 21 days	Observation until laboratory values return to Grade 1
Grade 4	Discontinue study treatment	
Pulmonary Events if possibly Interstitial Lung Disease (ILD)		
All Grades	Temporarily interrupt study treatment pending the diagnostic evaluation. If the pulmonary adverse event is felt to be related to osimertinib, then permanently discontinue osimertinib.	Unexplained dyspnea, either new or progressive, should be thoroughly evaluated. Where ILD is suspected, administer corticosteroids at a dose of 1 to 2 mg/kg/day prednisone equivalents for Grade 2 or greater pneumonitis, followed by corticosteroid taper.
Cardiac		
Grade 3	QTc interval greater than 500 msec on at least 2 separate ECGs	Withhold osimertinib until QTc interval is less than 481 msec or recovery to baseline if baseline QTc is greater than or equal to 481 msec, then restart at a reduced dose (40 mg)
Grade 4	QTc interval greater than 500 msec or > 60 msecs from baseline and with signs/symptoms of serious arrhythmia	Permanently discontinue osimertinib
Management of elevated creatine kinase: please check for drug-drug interactions and refer to appendix 2 for potential drug-drug interactions		
Grade 1	None	Observation (assess for drug-drug interactions contributing to elevation. Please refer to appendix 2)
Grade 2	None	Observation (assess for drug-drug interactions contributing to elevation. Please refer to appendix 2)

40

The information contained in this document is regarded as confidential, and may not be disclosed to another party unless such disclosure is required to initiate the study, to conduct study-related activities, or to comply with national, state, or local laws and regulations. Written authorization from the coordinating site and sponsor is required for disclosure otherwise.

Grade 3	Study treatment interruption for up to 21 days	Observation until laboratory values return to Grade 1 (assess for drug-drug interactions contributing to elevation. Please refer to appendix 2)
Grade 4	Discontinue study treatment	Discontinue study treatment
Ocular		
	Corneal ulceration	Permanently discontinue osimertinib
Grade > 3 or eye symptoms that are clinically significant and/or persistent (>7 days)	Referral to ophthalmologist	Permanently discontinue osimertinib
Grade 4	Referral to ophthalmologist	Permanently discontinue osimertinib
Other		
Grade ≥ 3 adverse event	If Grade 3 or higher adverse reaction improves to grade ≤ 1 after withholding of osimertinib for up to 21 days	Osimertinib may be restarted at the same dose (80 mg) or a lower dose (40 mg) at the discretion of the investigator
	If grade 3 or higher adverse reaction that does not improve to grade ≤ 1 after withholding for up to 21 days.	Permanently discontinue osimertinib

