16.1 Adverse Events

An adverse event (AE) is any untoward medical occurrence in a subject receiving study drug and which does not necessarily have a causal relationship with this study treatment. For this protocol, the definition of AE also includes worsening of any pre-existing medical condition. An AE can therefore be any unfavorable and unintended or worsening sign (including an abnormal laboratory finding), symptom, or disease temporally associated with the use of study drug, whether or not related to use of the study drug. Abnormal laboratory, physical exam or vital sign findings without clinical significance (based on the PI's judgment) should not be recorded as AEs

From the time that the subject signs the informed consent form through the End of Study Treatment visit (as defined in Section 8.3), all AEs must be recorded in the subject medical record and adverse events case report form.

AEs will be assessed according to the CTCAE version 4.03. If CTCAE grading does not exist for an AE, the severity of the AE will be graded as mild (1), moderate (2), severe (3), life-threatening (4), or fatal (5).

Attribution of AEs will be indicated as follows:

- Definite: The AE is clearly related to the study drug
- Probably: The AE is likely related to the study drug
- Possible: The AE may be related to the study drug
- Unlikely: The AE is doubtfully related to the study drug
- Unrelated: The AE is clearly NOT related to the study drug

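### No drug action is attached to Hy's Law, so the dose rules let a confirmed, drug-related case restart osimertinib at 80 or 40 mg

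*Combined protocol and SAP*

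**What the plan says.** **Dose rules (section 9.1.1).** Item 1 interrupts treatment for a related grade 3 or intolerable grade 2 event and bars restart until it is at grade 1 or less. Item 2: "If grade 3 or intolerable adverse event does not resolve with 21 days, patient should permanently discontinue study therapy". Item 3, for a first such event resolved within 21 days: "patient may restart at 80 mg dose level or 40 mg dose delay (at the discretion of the treating physician"). Item 4 sends a second event to 40 mg, and item 5 stops treatment for an event at 40 mg. Item 6 lists the events that end treatment; it opens "Patients experiencing corneal ulceration (any grade), interstitial lung disease (ILD") and adds QTc prolongation with signs or symptoms of serious arrhythmia. Hy's Law is not on the list.

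**Table 3 (section 9.1.2).** The liver row is headed "Hepatic Transaminases and/or total bilirubin: please refer criteria for" Hy's Law, with a pointer to Appendix 3. Its actions go by grade: none at grades 1 and 2, interruption for up to 21 days at grade 3, discontinuation at grade 4. The ILD row is built differently. It begins "Temporarily interrupt study treatment pending the diagnostic evaluation" and requires a permanent stop if the event is judged related.

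**Appendix 3.** Section 2 defines a potential case as ALT or AST at least 3 x ULN with total bilirubin at least 2 x ULN. Section 4.2 requires notification of AstraZeneca, contact with the Study Physician to agree follow-up, monitoring, work-up and CRF modules, with an SAE report if serious. Section 5 sets a review contact no later than 3 weeks after detection. A confirmed case is then reported as an SAE with causality assigned as related.

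**The concern.** The protocol runs a formal causality review for combined transaminase and bilirubin rises but attaches no dosing consequence to the answer. An investigator who follows the written rules exactly could re-expose a patient at full dose after an event that the plan itself classes as serious and caused by the drug. Restart could even come before the review has decided the cause. For three other toxicities (ILD, corneal ulceration, QTc prolongation with serious arrhythmia) the plan does not leave the stop to judgement. What is at stake is the safety of individual patients; the response-rate test is not affected as designed.

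**Working it through.** **1. Tracing a confirmed case through the text.** Take a patient on 80 mg with a first grade 3 liver event that meets potential Hy's Law criteria and is later agreed to have no cause except osimertinib.

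| Provision | What it requires of the drug |
|---|---|
| Table 3 liver row, grade 3 | Interrupt, up to 21 days |
| Appendix 3, 4.2 | Nothing stated |
| Appendix 3, 5 (confirmed, related) | Nothing stated; SAE report and causality only |
| 9.1.1 item 6 | Does not apply; Hy's Law not listed |
| 9.1.1 item 2 | Stop only if unresolved at 21 days |
| 9.1.1 items 1 and 3 | Once at grade 1 or less within 21 days, may restart at 80 or 40 mg |

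Appendix 3 sections 6 and 7 either call for no action (no significant change) or lead back to section 4.2. No step in the visible text blocks the restart.

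**2. Timing.** Assume the hold starts at detection. The review contact is due by day 21. If the event resolves on day d and the drug restarts that day, the longest time on drug before the deadline is 21 − d:

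- d = 7: 14 days
- d = 14: 7 days
- d = 21: 0 days

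These are maxima. They assume that contact happens on the last permitted day and that the physician chooses to restart at once.

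**3. Effect of the fix on the primary endpoint.** Section 22.4.2 counts a patient who stops before confirmation of response as a non-responder. The first scan is at cycle 3 day 1, day 2 × 28 + 1 = 57. The earliest confirmation at 4 weeks is day 57 + 28 = 85, and the next scheduled scan, cycle 5 day 1, is day 4 × 28 + 1 = 113. Only a stop before about day 85 to 113 could cost a response.

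For the Simon design (stop at 3 or fewer of 17; success at more than 10 of 37), with X1 ~ Bin(17, p) and X2 ~ Bin(20, p):

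P(success) = Σ over x from 4 to 17 of P(X1 = x) × P(X2 > 10 − x).

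- Check against the plan: p = 0.20 gives type I error 0.0948 and early stopping probability 0.5489; p = 0.40 gives power 0.903, so type II error 0.0967. All match section 22.4.2.
- Suppose the fix adds k non-responders (assumed), spread at random: p = 0.40 × (37 − k)/37. For k = 0, 1, 2, p = 0.400, 0.389, 0.378 and power is 0.903, 0.881, 0.854.
- Other placements for k = 1 and 2: all in stage 1 as fixed non-responders, 0.875 and 0.841; all taken from would-be responders, p = (14.8 − k)/37, 0.839 and 0.749.

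The random-spread figures are an illustrative average case, not a bound. Added non-responders cannot raise the type I error.

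**The case against.** The best reply is that restart is a permission and that other safeguards surround it. Section 9.1.2 says "investigators should manage toxicities per institutional standards and the specific clinical circumstances". Section 13.1 lists abnormal laboratory values and unacceptable toxicity as grounds for withdrawal. Appendix 3 makes Study Physician contact mandatory and brings AstraZeneca safety staff into the review. Section 2.4 reports no apparent association with drug-induced liver injury. All of this stands and limits the likely harm. But each safeguard allows a stop without requiring one, and Appendix 3 does not name dosing among the matters to be agreed.

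A second reply is that the schema figure in 9.1.1 is not shown, nor are the AstraZeneca processes cited for SAE reporting. That is a true limit. The finding concerns the visible text; the figure's heading covers grade 3 or intolerable grade 2 events in general.

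Three stronger readings are tempting and are not supported:

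- A reader might infer that a Hy's Law case can sit at grade 2 and continue with no dose change. That depends on CTCAE 4.03 limits that the documents do not print.
- A reader might use the Table 3 catch-all row for other grade 3 or higher events ("Osimertinib may be restarted at the same dose (80 mg) or a lower dose (40 mg) at the discretion of the investigator") as a second route to restart, by grading Hy's Law as a separate event under section 16.1 ("If CTCAE grading does not exist for an AE, the severity of the AE will be graded as mild"). Liver events have their own row, which stops treatment at grade 4, so this is strained. Item 3 carries the point alone.
- A reader might take the ILD row as evidence of equal risk. Section 2.4 gives ILD in 3.5% of 833 patients, fatal in 0.6%, against no apparent liver-injury signal. The row is a model for wording only.

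**Conclusion.** The gap is real in the text: confirmed, drug-related Hy's Law carries no mandatory hold or stop, and items 1 and 3 of 9.1.1 permit restart at 80 or 40 mg after a first grade 3 event that resolves within 21 days. Restart can precede the causality deadline by at most 14, 7 or 0 days for resolution on day 7, 14 or 21. It would be wrong to infer that the plan directs re-exposure, or that many patients are at risk: the number cannot be derived and is probably very small. The conclusion rests on the visible text of 9.1.1, Table 3 and Appendix 3. This is a cheap safety improvement; it does not weaken the trial's primary analysis.

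**What to change.** 1. **Confirmed Hy's Law.** Add it to 9.1.1 item 6 and to the Table 3 liver row as permanent discontinuation without rechallenge. State that this overrides item 3 (and item 4, which would otherwise lead to 40 mg after a second event).
2. **Potential Hy's Law newly met on treatment.** In the Table 3 liver row and Appendix 3 section 4.2, interrupt osimertinib pending the Appendix 3 review. If another cause is agreed, resume under the existing dose rules. A hold made solely for the review should not count toward the 21-day interruption limit in section 9.1; item 2 still governs grade 3 events that have not resolved. Exempt Appendix 3 section 6 and 7 cases with no significant change.

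The exception to the limit matters because a hold from detection to the 3-week contact uses all 21 days, and a patient with another cause could lose therapy. Liver tests during the hold should come from the monitoring that section 4.2 already requires. Day-1 draws are 28 days apart (21 to 35 with the 7-day window), too sparse to guide it.

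**Cost.** A few sentences through a routine amendment (IRB approval under section 18.5, with the CPC informed under 18.2). The downside is an occasional interruption in a patient whose rise has another cause and, rarely, an earlier stop counted as a non-response. Any power figure quoted for that should be labelled illustrative.
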